13.4.2 Coronary artery bypass grafting (CABG)

1. Standardized Method: Under general anesthesia, pulmonary artery pressure is monitored using transesophageal echocardiography and a Swan-Ganz catheter. After median sternotomy, the left internal mammary artery and right gastroepiploic artery or right internal mammary artery are harvested using a skeletonization technique. Heparin (150 U/kg) is administered intravenously. A composite graft is created by connecting the right gastroepiploic artery or right internal mammary artery to the side of the left internal mammary artery. The left anterior descending artery is anastomosed using a local stabilizer on a beating heart, followed by anastomosis to the branches of the left circumflex artery and right coronary artery territory. After completing the anastomosis, protamine (0.15 mg/kg) is administered for neutralization, and the patency of the anastomosis is checked using a flowmeter before completing the surgery.
2. Distinguishing the Bypass Site from the Gene Injection Site: Although not strictly necessary for safety evaluation, for future efficacy assessments, the entire myocardial region will be segmented and evaluated by echocardiography, myocardial SPECT, and cardiac MRI. Therefore, it is expected to be possible to distinguish the bypass site from the gene injection site. This distinction will be particularly useful for efficacy evaluation in subsequent Phase 2 and Phase 3 studies involving control groups.
3. Target Group: All study subjects will undergo the procedure on Day 0, with VM202RY injected into the distal portion of the myocardium showing incomplete revascularization.
4. The goal is to confirm patency on angiography performed before discharge after surgery.

5. Surgery will primarily be performed on a beating heart. Patients requiring cardiopulmonary bypass due to hemodynamic instability will be excluded.

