14.2 Step 1: coronary artery bypass surgery and gene therapy period

During the gene therapy period (7 days), the subjects will be hospitalized for treatment.

1) Clinical evaluation

Symptoms of ischemic heart disease and physical examination: vital signs, auscultation findings, and other clinical examination findings. Canadian angina class, New York heart association functional classification

2) Laboratory test

(Note: The test results for anti-HGF antibodies and HGF protein in blood will be recorded in the case report form after the completion of the 24-week follow-up period.)

1. General Blood Tests

- Common Tests
 - Days 0, 1, 2, 5, and 7: CBC with differential count

- Days 1 and 7: ESR
- Additional tests by study group: None

2. General Chemistry Tests

- Days 1, 2, 5, and 7: Admission battery with electrolytes, lipid battery
- Days 1 and 7: CRP

3. Urinalysis: performed on Days 1, 5, and 7

4. ECG: follow-up on Days 0, 1, 2, 5, and 7

5. Cardiac Enzymes (CK/CK-MB, LDH, Troponin I): performed on Days 0, 1, 2, 5, and 7

6. Chest X-ray: performed on Days 0, 1, 2, 5, and 7

7. Echocardiography (TTE): performed on Day 7

8. Holter Monitoring: performed on Day 7

9. Blood Sampling for HGF Protein: performed on Day 7

(Tests on the day of surgery [Day 0] should be performed prior to the procedure.)

3) Intensive care and monitoring

1. Day of Surgery (POD#0 DAY): After surgery, the patient is transferred to the intensive care unit (ICU) with ventilatory support. The amount of bleeding is monitored through chest tubes inserted into the pericardium, mediastinum, and left and right pleural cavities in the operating room. Reoperation is considered in cases of significant bleeding (e.g., 500cc within 1 hour, 400cc/hr over 2 hours, or 300cc/hr over 3 hours). Continuous monitoring of systemic arterial pressure and pulmonary arterial pressure is performed. Medications (inotropics or vasodilators) and fluids are administered as needed based on hemodynamic status. Transient arrhythmias such as ventricular arrhythmias or atrial fibrillation are monitored via 24-hour ECG, and antiarrhythmic therapy (e.g., amiodarone) is administered if necessary. The patient's level of consciousness is assessed after awakening from anesthesia.

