2. POD#1 DAY: If there is no bleeding and the hemodynamic status is stable, the ventilator is removed. Intravenous vasodilators are switched to oral medications. Continuous monitoring of systemic and pulmonary arterial pressure and ECG continues. Once hemodynamic stability is confirmed, the patient is transferred to the general ward and monitored with a 24-hour ECG.
3. POD#2 DAY: Under 24-hour ECG monitoring, the patient begins light physical activity in the ward. Chest tubes are removed if daily drainage is less than 1cc per kg of body weight.
4. POD#3 ~ 6 DAY: While continuing 24-hour ECG monitoring, physical activity is gradually increased in the ward. The patient is observed for allergic reactions possibly related to gene therapy, such as skin rashes, angioedema, or bronchospasm.
5. POD#7 DAY: Holter monitoring is performed, and transthoracic echocardiography is conducted to evaluate cardiac function. If no abnormalities are found, discharge is considered.

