14.3 Step 2: follow-up period

1) Follow-Up Assessment Schedule

A total of 24 weeks of follow-up evaluations will be conducted. Based on the day of surgery (Day 0), follow-up visits will occur at Weeks 2, 4, 8, 12, and 24. The visit window will be ± 4 days for Weeks 2 and 4, and ± 7 days for Weeks 8, 12, and 24.

2) Clinical Evaluation

1. Assessment of medication status
2. Evaluation of symptoms and physical examination related to ischemic heart disease: vital signs, auscultation findings, and other clinical signs; Canadian Cardiovascular Society (CCS) classification; New York Heart Association (NYHA) functional classification

3) Laboratory tests

(Note: The results of anti-HGF antibody and HGF protein levels in blood will be recorded in the case report form after completion of the Week 24 follow-up period.)

1. Complete Blood Count: CBC with differential count, ESR: Performed at Weeks 2, 4, 12, and 24.
2. General Chemistry Tests: Admission battery with electrolytes, lipid battery, CRP: Performed at Weeks 2, 4, 12, and 24.
3. Urinalysis: Performed at Weeks 2, 4, 12, and 24.
4. Cardiac Enzymes: CK, CK-MB, LDH, Troponin I: Performed at Weeks 2, 4, 12, and 24.
5. Chest X-ray: Performed at Weeks 2, 4, 12, and 24.
6. ECG: Performed at Weeks 2, 4, 8, 12, and 24.
7. Echocardiography (TTE): Performed at Weeks 12 and 24.
8. Coronary Angiography (CAG): Performed at Week 24.
9. Myocardial SPECT and Cardiac MRI: Performed at Weeks 12 and 24.
10. Blood Sampling for Anti-HGF Antibody: Performed at Weeks 2, 4, and 24.
11. Blood Sampling for HGF Protein: Performed at Weeks 2, 4, 8, 12, and 24. If two consecutive results are negative, testing will be discontinued, and results will be considered negative.
12. Holter Monitoring: Performed at Weeks 2, 4, 12, and 24.
13. Fundus Photography: Performed at Weeks 2, 4, 12, and 24.
14. Tumor Marker Tests (CEA, PSA, alpha-fetoprotein, CA19-9, CA125) and Fecal Occult Blood Test: Performed at Weeks 12 and 24.

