14.4 Step 3: long-term follow-up

Long-term follow-up will be conducted to monitor for serious adverse events such as cancer occurrence and survival status at 1, 2, 3, 4, and 5 years after administration of VM202RY. If in-person visits are not possible, follow-up may be conducted via telephone. The timing of each visit should occur at one-year intervals from the date of investigational drug administration, within a \pm 30-day window. The sponsor shall report the annual telephone follow-up results to the Ministry of Food and Drug Safety (MFDS) each year. Additionally, any serious adverse events related to the investigational drug that occur during this period must be promptly reported to the MFDS.

15. Adverse events and precautions for use of VM202RY

Various methods have been attempted to deliver the therapeutic gene to the target myocardium, but none have yet secured a definitive advantage. Therefore, this research team aims to evaluate the safety of VM202RY by directly injecting it into the myocardium after performing standard coronary artery bypass graft (CABG) surgery. The target patients are those who are candidates for CABG and are expected to benefit most from gene therapy—specifically those with reversible myocardial regions or areas with incomplete reperfusion due to issues with the target coronary artery or graft vessels during surgery.

To date, no adverse effects have been reported in preclinical or clinical studies indicating that injection of the hepatocyte growth factor gene into the myocardium—or similar gene therapies—has a direct negative impact on CABG procedures

16. Discontinuation and withdrawal of subjects from the clinical trial

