17.4.3 Methods and criteria for efficacy evaluation

- 1) Changes in cardiac function

Changes in cardiac function can be evaluated using the left ventricular ejection fraction (LVEF) measured by cardiac MRI, myocardial SPECT, and echocardiography. Differences between treatment groups before and after VM202RY administration will be tested using the Kruskal-Wallis test.

Cardiac MRI methods and criteria

Analysis will follow the standard cardiac MRI protocols of the Department of Radiology at Seoul National University Hospital, using an appropriate segment model based on the patient's heart size. Parameters evaluated will include left ventricular volume (mL), wall motion index, myocardial thickness (mm), and LVEF (%). Comparisons will be made between baseline and follow-up measurements for each patient, as well as between treatment groups.

Myocardial SPECT methods and criteria

A 20-segment model, similar to the MRI analysis, will be used. Blood flow in each coronary artery distribution area will be assessed using a Bull's-eye view. Perfusion (%) will be evaluated from stress and rest images obtained using Dipyridamole. Additionally, the degree of systolic wall thickening (%), left ventricular volume, and function over time will be compared between groups. Left ventricular volume (mL), ejection fraction (%), and cardiac output (mL) obtained from SPECT will be used as supplementary data. Wall motion indices before and after surgery will be compared. Criteria for determining perfusion deficits and reversibility will follow established standard methods.

Echocardiography methods and criteria

From transthoracic echocardiography, left ventricular diameter (mm), ejection fraction (%), and wall thickness (mL) will be measured and compared with follow-up results after surgery. The Wall Motion Score Index will be calculated by dividing the myocardium into 16 segments and assigning a score to each area based on motion: [1 = normal, 2 = hypokinetic, 3 = akinetic, 4 = dyskinetic]. The total score for the entire myocardium and the right coronary artery region will be averaged by the number of segments.

- 2) Size of viable myocardium

Using cardiac MRI, the myocardial thickness at the gene injection site, the extent of late gadolinium enhancement, and local wall motion strength will be evaluated. Differences between groups before and after VM202RY administration will be tested using the Kruskal-Wallis test.

3) Improvement in Myocardial Ischemia

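### The only regional echocardiographic wall motion index is fixed to the right coronary region, although the plan does not confine injection to that territory

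*Combined protocol and SAP*

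**What the plan says.** Under the echocardiography methods in 17.4.3, the myocardium is divided into 16 segments, each graded 1 (normal) to 4 (dyskinetic), "assigning a score to each area based on motion". The Wall Motion Score Index is then formed as follows: "The total score for the entire myocardium and the right coronary artery region will be averaged by the number of segments". No reason is given for choosing the right coronary region, and the segments belonging to it are not listed.

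The neighbouring SPECT rule is not limited to one territory: "Blood flow in each coronary artery distribution area will be assessed". Later in 17.4.3, MRI has measures at the gene injection site (thickness, late enhancement, local wall motion) and SPECT has perfusion in the injection region.

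The Synopsis lists regional cardiac function by MRI, SPECT and echocardiography as part of a secondary efficacy endpoint. Section 13.4.2 item 2 says that segmental evaluation by the same three methods should allow the bypass site to be told apart from the injection site. It qualifies this: "Although not strictly necessary for safety evaluation, for future efficacy assessments".

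**The concern.** A regional index helps assess an injected product only if its region contains the injected muscle. Here the region is fixed for everyone, while the injection follows whichever vessel could not be grafted. In a subject injected in another territory, the right coronary index cannot register a change at the injection site. It can, however, move because a graft was placed in the right coronary territory, which 13.4.2 item 1 names among the graft targets. A report of regional function by echo would then describe the surgery rather than the injection. At stake is how the echo part of one secondary endpoint is read, not the safety findings or the tolerated dose.

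**Working it through.** The plan states no figure to reproduce. The check is a comparison of sections, followed by a short illustration.

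**Where the injection goes**

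- 11.1 item 3: bypass judged infeasible in some perfusion areas; no territory named.
- 11.3 items 1 and 2: refers to the target coronary artery and the vessel's condition; no territory named.
- 13.1: 4 or 8 sites in the affected region.
- 13.3: within the area of incomplete revascularization, for all three cohorts.
- 13.4.2 item 3: the distal part of the incompletely revascularized myocardium.
- 13.4.3: distal to the incompletely revascularized vessels, on both sides of the vessel.
- 15: target patients include those with "areas with incomplete reperfusion due to issues with the target coronary artery or graft vessels during surgery"; again no territory.

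Apart from 17.4.3, the available text mentions the right coronary artery only in 13.4.2 item 1, as a graft territory alongside the left anterior descending and left circumflex. A subject injected in either of those two territories is therefore within protocol.

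**What each method measures at the injected site**

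| Method | Tied to injection site or region? |
|---|---|
| MRI | Yes |
| SPECT | Yes |
| Echo wall motion index | No: global and right coronary only |

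**Illustration for one subject injected outside the right coronary region**

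Suppose k injected segments each improve by one grade and nothing else changes. The documents do not give k; I take 1 to 4.

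- Change in global index = k/16: 1/16 = 0.0625, 2/16 = 0.125, 3/16 = 0.1875, 4/16 = 0.25.
- Change in right coronary index = 0, because none of the changed segments is in it.
- Change in a mean over the injected segments = k/k = 1.0.

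Worked case, k = 3. At baseline three injected segments score 2 and the other 13 score 1.

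- Global: (3×2 + 13×1)/16 = 19/16 = 1.1875, falling to 16/16 = 1.0, a change of 0.1875.
- Right coronary: 1.0 before and after, a change of 0.
- Injected segments: 2.0 falling to 1.0, a change of 1.0.

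These contrasts follow from the definition of a mean. They show which index can respond and are not estimates of any effect.

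**The case against.** The case against giving this much weight is strong, and most of it stands.

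- **The data are not lost.** All 16 segments are scored, so an injected-region mean could be derived later. True. But the trial is open-label, and segments chosen after follow-up echocardiograms are seen could be chosen to suit the result. That is the reason to define the index beforehand.
- **MRI and SPECT already cover the injection site.** True, at Weeks 12 and 24. A reader might infer that the trial has no regional measure of injected muscle; the MRI and SPECT rules in 17.4.3 show otherwise.
- **The index feeds no test.** In 17.4.3 and the Synopsis, the Kruskal-Wallis test for cardiac function is attached to ejection fraction. Section 17.4 calls efficacy exploratory. This stands and limits the consequence.
- **It may be a slip of wording.** The same paragraph gives echo wall thickness in mL, so slips do occur. The documents do not settle it. Either way the sentence needs correcting or explaining.

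A reader might also infer a distinct gap on Day 7, since 14.2 lists "Echocardiography (TTE): performed on Day 7" while 14.3 has "Myocardial SPECT and Cardiac MRI: Performed at Weeks 12 and 24". The documents do not support treating that as a missed efficacy assessment. Section 14.2 says that on that day "transthoracic echocardiography is conducted to evaluate cardiac function" and then links the result to considering discharge. No section makes Day 7 an injection-site efficacy time point, and 17.3.3 says that most patients have impaired cardiac function because of the nature of the surgery.

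**Conclusion.** The point holds, with low weight. As written, the only regional echo index covers a territory to which injection is not confined. For any subject injected elsewhere, it does not serve the echo part of the regional-function endpoint.

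The number affected cannot be derived from the documents. It runs from none to every subject dosed (9 planned, up to 18 if dose-limiting toxicity occurs, plus replacements for dropouts). A reader might want a probability that at least one subject is affected, but the documents give no distribution of injected territories, so any such figure would only restate an assumption. If every injection falls in the right coronary territory, the rule does no harm.

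The effect is confined to one exploratory echo summary. Safety and dose-escalation conclusions are unaffected. Nor would a corrected index isolate a product effect, since there is no control arm; 13.4.2 item 2 itself expects the separation of bypass and injection sites to be most useful in later controlled trials.

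The conclusion assumes that no part of the protocol outside the available text limits the injected territory.

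**What to change.** In 17.4.3, define the regional echo index as the mean wall motion score over each subject's injected segments. Identify those segments from the surgical record, map them to the 16-segment model before any follow-up echocardiogram is read, and use the same segments at baseline and every later echo. Keep the global average.

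If the right coronary region was meant to be the injected region, or the term is a wording error, reconcile 17.4.3 with 11.1, 11.3, 13.1, 13.3 and 13.4.3 instead.

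The cost is about one sentence of text, plus recording the injected location at surgery and mapping it to the echo segments. The MRI and SPECT measures already need that location. The mapping is nevertheless a separate step, because SPECT uses 20 segments and the MRI model is chosen by heart size. The case report form is not in the documents, so whether it already has a field for this is unknown. No new scans or segment readings are required.

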17.5 Secondary endpoint: HGF plasma concentration

In typical phase 1 clinical trials, the pharmacokinetic characteristics of a drug are observed to assess the relationship between the administered dose, blood concentration, and any resulting clinical effects or adverse reactions. However, since the investigational product in this study is a gene therapy, it is not feasible or clinically meaningful to measure the conventional pharmacokinetic parameters used in standard phase 1 drug trials. Therefore, plasma HGF concentration will be measured and observed, and its correlation with the presence, severity, and pattern of adverse events will be evaluated.

17.6 Secondary endpoint: HGF antibody formation induced by VM202RY injection

The presence of HGF antibodies in the blood will be assessed using the ELISA method. A preliminary evaluation will be conducted to determine whether there is a correlation between HGF antibody formation and the improvement in myocardial function, by comparing subjects who showed improved cardiac function with those who did not.

18. Definition and reporting of adverse events

All adverse events that occur after the subject has signed the informed consent form must be recorded in the case report form (CRF). During the trial period, if the investigator becomes aware of any significant risk factors related to the safety of the investigational product, contraindicated concomitant medications, adverse events, or precautions for use, this information must be reported to the sponsor.

18.1 Definition of adverse events

An adverse event is defined as the occurrence or worsening of any of the following:

- 1) All symptoms and signs not related to the primary diagnosis, or symptoms and signs that are aggravated and related to the primary diagnosis
- 2) Clinically significant abnormalities in laboratory test results
- 3) Abnormal findings from physical examinations

These events must be recorded in the CRF even if they are not considered related to the investigational product (i.e., "possibly related" events should be recorded).

The investigator should assess adverse events according to the WHO Toxicity Scale. If the WHO scale is not applicable, the severity of adverse events should be evaluated using Spilker's three-grade classification system.

Grade	Criteria
Mild	When no treatment is required, and the subject's normal daily life (functions) is not significantly impaired
Moderate	When the subject's normal daily life (functions) is significantly impaired, treatment may be required, and recovery occurs after treatment
Severe	When a severe adverse reaction requires intensive medical intervention and leads to lasting aftereffects, or in cases of life-threatening adverse events

The investigator shall evaluate the causality between the adverse event and the investigational product based on the following criteria:

- 1) Definitely related
 - There is evidence that the investigational product was administered.
 - The temporal relationship between administration and the adverse event is appropriate.
 - The adverse event is more likely explained by administration of the investigational product than by any other cause.
 - The adverse event resolves upon discontinuation of the investigational product.
 - The adverse event reappears upon rechallenge (if performed).
 - The adverse event is consistent with known information about this product or products of the same class.
- 2) Probably related
 - There is evidence that the investigational product was administered.
 - The temporal relationship between administration and the adverse event is appropriate.
 - The adverse event is more likely explained by administration of the investigational product than by other possible causes.
 - The adverse event resolves upon discontinuation of the investigational product.
- 3) Possibly related
 - There is evidence that the investigational product was administered.

- The temporal relationship between administration and the adverse event is appropriate.
- The adverse event is equally likely to be caused by the investigational product as by other possible causes.
- The adverse event resolves upon discontinuation of the investigational product (if done).

4) Probably not related

- There is evidence that the investigational product was administered.
- There is a more likely alternative cause for the adverse event.
- The adverse event does not resolve or shows an unclear outcome upon discontinuation (if done).
- The rechallenge result is negative or unclear (if done).

5) Definitely not related

- The subject did not receive the investigational product, or
- The temporal relationship between administration and the adverse event is not appropriate, or
- There is a clear alternative explanation for the adverse event.

If a dose-limiting toxicity (DLT) or an unexpected Grade 3 or higher adverse event occurs, the causality between the adverse event and the investigational product must be assessed by two or more investigators.

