13.4.6 Basis for dose setting and dose escalation

1) Timing of dose escalation

- (1) After observing patients receiving the same dose for 4 weeks (4 weeks after administration of the investigational drug), if the criteria for dose escalation discontinuation are not met, the dose will be increased to the next level.

Criteria for Discontinuing Dose Escalation

- ① Dose-limiting toxicity (DLT) occurs in 2 out of 3 patients.
- ② A patient develops cancer or proliferative retinopathy attributable to VM202RY gene therapy.
- ③ If DLT occurs in 1 out of 3 patients at the same dose, an additional 3 patients will be tested at that dose, and if DLT occurs in 1 out of these 3 additional patients (i.e., 2 out of 6 patients), dose escalation will be discontinued.

2) Additional subject enrollment

- (1) If dose-limiting toxicity (DLT) occurs in 1 out of 3 patients, an additional 3 patients will be enrolled at the same dose level. If no DLT occurs in these additional 3 patients, dose escalation to the next level will proceed.
- (2) If any subjects drop out during the follow-up period (24 weeks) within the same dose group, additional subjects will be enrolled to replace the dropouts.

3) Basis for dose setting

The dose was set based on the results of preclinical studies of VM202RY and the preclinical results conducted by Morishita's group, following the typical dose-setting criteria applied in Phase 1 clinical trials.

(1) Basis from toxicity study results

In toxicity tests using rats and mice, no toxic changes were observed even at doses of 13.68 mg/kg in repeated dose toxicity tests (400 times the maximum clinical dose of 2 mg/human), 6.84 mg/kg in single dose toxicity tests (200 times the maximum clinical dose), 1.14 mg/kg in immunotoxicity tests, and 6.84 mg/kg in genetic and reproductive toxicity tests (200 times the maximum clinical dose). These results suggest that the clinical doses of 0.5, 1, and 2 mg used in this clinical trial are safe, being at least 200 times and up to 400 times lower than the tested toxic doses.

(2) Basis from efficacy study results

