According to the WHO Toxicity Scale, toxicities of Grade 3 or higher are generally considered dose-limiting. However, since this clinical trial includes surgery, the following reactions caused by surgery are excluded from the DLT (Dose-Limiting Toxicity) evaluation:

Adverse events caused by coronary artery bypass graft (CABG) surgery are excluded from the DLT evaluation.

1. Hematology

- Hemoglobin: Decrease due to surgical bleeding that recovers with transfusion.
- Hemorrhage: Common post-operative complication. However, persistent bleeding at the gene injection site should result in discontinuation of dose escalation.

2. Gastrointestinal

- Bilirubin: Elevation up to 10.6 due to intra-body retention of hematoma after surgery is considered a normal response.
- GOT/GPT (AST/ALT): Levels up to 125/350 are excluded if attributable to transfusion or myocardial ischemia.

3. Renal / Bladder

- Proteinuria: If caused by pre-existing diabetes or renal failure.
- Hematuria: If caused by trauma during Foley catheter insertion.

4. Pulmonology: Findings due to decreased cardiac function.

5. Fever: Fever above 39°C lasting less than 24 hours (unless associated with pulmonary complications or infection).

6. Allergic Reactions: When the cause is clearly identified, such as contrast agents, antibiotics, or blood transfusion.

7. Cardiac

- Rhythm: Arrhythmias are unavoidable due to surgical dissection of the myocardium. While ventricular arrhythmias may occur due to reperfusion of chronically ischemic areas, establishing a direct association with gene injection is difficult. However, in the interest of patient safety, WHO Grade 3 criteria will be followed and dose escalation will be discontinued.
- Cardiac Function: Most patients have impaired cardiac function due to the nature of cardiac surgery; thus, excluded from DLT evaluation.
- Pericarditis: Most cases involve post-operative accumulation of blood or fluid in the pericardial space. Surgery may be necessary, but dose escalation will be discontinued only if bleeding is confirmed at the gene injection site.

2) TD (tolerated dose) evaluation

Subjects are enrolled sequentially, starting from Step 1, to determine the tolerated dose as follows:

1. Step 1: Three subjects are enrolled. DLT (Dose-Limiting Toxicity) is evaluated 4 weeks after the third subject is dosed.
 - 1-1. If no DLTs occur in any of the 3 subjects (0/3) → Proceed to Step 2 and enroll 3 more subjects (A)

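### The causality scale in 18.1 asks for resolution on stopping a product that is injected only once, so a lasting event judged more likely due to VM202RY fits no level

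*Combined protocol and SAP*

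**What the plan says.** Section 18.1 has the investigator rate causality on five levels, each with its own list of criteria. Levels 1 (Definitely related) and 2 (Probably related) both contain the line "The adverse event resolves upon discontinuation of the investigational product", with no condition attached.

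Elsewhere on the scale, lines that may not apply are made conditional. The level 1 rechallenge line carries a condition: "The adverse event reappears upon rechallenge (if performed"). So does the level 3 (Possibly related) discontinuation line: "The adverse event resolves upon discontinuation of the investigational product (if done"). Level 4 (Probably not related) has a conditional line that runs the other way: the event does not resolve, or its outcome is unclear, after stopping.

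The likelihood lines also differ. Levels 1 and 2 need the product to be the more likely explanation. Level 3 needs "The adverse event is equally likely to be caused by the investigational product as by other possible causes". Level 4 needs a more likely alternative. Level 5 (Definitely not related) is met by no dosing, unsuitable timing or a clear alternative, and is the only level whose lines are joined by an explicit or.

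On dosing, 13.4.2 says "All study subjects will undergo the procedure on Day 0", and 13.4.3 describes one set of injections after the grafting. No further administration is planned.

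**The concern.** A criterion about stopping treatment suits a drug given repeatedly. Here the whole dose is in the myocardium before any event can be observed, so the criterion either cannot be met or is met only by calling the end of the injection a discontinuation. On both readings, an event that the investigator thinks is more likely due to the product, and that does not go away, has no place on the scale.

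Safety is the primary endpoint, and several product-specific harms that 18.2 anticipates may well not resolve: retinal lesions, myocardial hemangioma, heterotopic tissue in the heart, tumour progression. Attribution also informs later judgements. One criterion for stopping escalation in 13.4.6 is "A patient develops cancer or proliferative retinopathy attributable to VM202RY gene therapy". Expedited regulatory reporting in 18.4 concerns adverse drug reactions, and 18.5 sets follow-up for reactions that are related or possibly related. If the scale offers no level for a lasting, product-attributed event, two assessors may record the same event differently.

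**Working it through.** No sample size, error rate or event count is involved, and the plan gives no figure to reproduce. The check sets the levels side by side and tests which profiles each one admits.

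**Inputs (18.1).**

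| Level | Likelihood line | Discontinuation line | Conditional? |
|---|---|---|---|
| 1 Definitely related | product more likely | resolves | no |
| 2 Probably related | product more likely | resolves | no |
| 3 Possibly related | equally likely | resolves | yes |
| 4 Probably not related | other cause more likely | does not resolve, or unclear | yes |
| 5 Definitely not related | not dosed, or wrong timing, or clear alternative | none | not applicable |

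The discontinuation line appears at 4 of the 5 levels and lacks a condition at 2 of those 4. Level 1 also asks that the event be consistent with known information on the product or its class.

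**Profiles.** Take a dosed subject with appropriate timing, no clear alternative explanation (so level 5 is out) and no rechallenge. Cross 3 likelihood judgements with 2 outcomes: 3 × 2 = 6 profiles. The lines within each of levels 1 to 4 are taken as joint requirements.

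**Two readings.** Reading A: completing the injection counts as discontinuation at every level. Reading B: discontinuation is not done, so conditional lines drop out and unconditional ones cannot be met.

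| Profile | Reading A | Reading B | After the fix |
|---|---|---|---|
| Product more likely, resolves | 2 (also 1 if consistent) | none | 2 (also 1 if consistent) |
| Product more likely, lasting | none | none | 2 (also 1 if consistent) |
| Equally likely, resolves | 3 | 3 | 3 |
| Equally likely, lasting | none | 3 | 3 |
| Other cause more likely, resolves | none | 4 | 4 |
| Other cause more likely, lasting | 4 | 4 | 4 |
| **Unfilled** | **3 of 6** | **2 of 6** | **0 of 6** |

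The lasting, product-more-likely profile is unfilled under both readings.

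**A partial repair.** Deleting the line at levels 1 and 2 alone fills one profile under A, leaving 3 − 1 = 2 of 6, because levels 3 and 4 still turn on resolution. Under B it fills both, leaving 2 − 2 = 0 of 6. The repair has to cover levels 1 to 4 to work on either reading.

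**The case against.** The strongest reply is that 18.1 never says all lines must hold. It asks for causality to be judged on the listed criteria, and a sensible investigator would pass over a line that cannot apply. For a DLT or an unexpected event of Grade 3 or higher, at least two investigators must assess causality. This has some force: joint requirement is the natural reading, not a stated one. But conditions were written on the neighbouring lines and left off these two, alternatives are spelled out only at level 5, and no fallback is given. Having two assessors does not help if each resolves the gap in a different way.

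The second reply is that little depends on the scale, and this stands. Adverse events are recorded whatever their relationship to the product and tabulated by dose group (17.3.3). MACE and injection complications are counted by occurrence. Serious events and MACE are reported regardless of relationship, apart from a narrow exception for IRB reporting (18.4). DLT status rests on grade and on the rule that "Adverse events caused by coronary artery bypass graft (CABG) surgery are excluded from the DLT evaluation", not on a causality level. Section 18.2 lists stroke, perioperative infarction and early postoperative death as surgical complications, so for many early events another cause will be judged more likely and the gap will not arise.

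A reader might infer that a lasting event would be pushed down to Possibly related. The documents do not say so: that level needs equal likelihood, and no default is named. A reader might also see a contradiction with the Spilker grade Severe, which covers an event that "requires intensive medical intervention and leads to lasting aftereffects, or in cases of life-threatening adverse events". Severity and causality are separate axes, an event can resolve and still leave aftereffects, and a life-threatening event qualifies as Severe without them. That is no contradiction.

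**Conclusion.** The criterion is wrong as written for a single-injection product, and the point is minor. Depending on how the end of dosing is read, 3 of 6 or 2 of 6 likelihood-by-outcome profiles have no level. These are counts of logical profiles, not event frequencies; the documents give no basis for estimating how often such events would occur.

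It is tempting to say that every gap falls where the injection is the more likely cause. That holds under reading B only; under reading A two of the three gaps lie elsewhere. A count of 1 of 6 is reached only by mixing the readings, with the injection counted as discontinued at levels 1 and 2 but not at levels 3 and 4.

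A reader might also infer that dose escalation or the tolerated dose would change. The documents do not support this, since the cancer and retinopathy stop refers to attribution without citing a level. What is established is that lasting events attributed to the product cannot be classified consistently, and that this may inform the stop in 13.4.6, drug-reaction reporting in 18.4 and follow-up in 18.5. The conclusion rests on reading the lines within each of levels 1 to 4 as joint requirements.

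**What to change.** Add one sentence to 18.1: VM202RY is given as a single injection session, so the discontinuation and rechallenge lines at levels 1 to 4 do not apply. At levels 1 and 2, delete the discontinuation line or mark it as applying only where applicable. A lasting event more likely due to the injection can then be rated Probably related, or Definitely related if it also agrees with what is known of the product or its class.

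The cost is a sentence and an edit to two lines. No test, visit or subject is added. The downside is that slightly more events may be rated as product-related.
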